2.5. Development of outcome measurements

EG will view 20% of unblinded data to determine which potential confounders to include in the outcome models, in the addition to those identified in advance, based on previous research. Section 3.1.1 provides further details on how confounders will be selected. The unblinded data will be split evenly between the MHP and usual care cohorts in order for EG to remain blinded to the treatment and control cohorts when analyzing outcomes.

EG will also create a model of the confounders of app usage to use in dose-response models and a propensity score matching model for the groups.

To allow EG to remain blinded to the final data, while performing these analyses, LH will generate random values of adherence, drawn from the distribution for the MHP cohort, for the usual care cohort. LH will run the outcome models on the full set of data and will report the results to EG for interpretation. EG will finish data analysis before being unblinded to the labels of the MHP and usual care cohorts.

2.6. Descriptive statistics for outcome measurements

The primary and secondary outcome measurements will be described in the main text of the manuscript. The exploratory outcomes will be described in the supplemental material. For continuous variables, the mean and standard deviation will be reported for the MHP and usual care cohorts. For binary variables, frequency and proportion will be reported.

2.7. Exploratory metric

As an exploratory metric, we may calculate the patient cooperativity index (PCI) (2), which accounts for how frequently participants take “app holidays,” extended breaks from using the app. The PCI is an odds ratio, where participants with a higher PCI are more likely to use the app one day after using it the previous day. In equation 2, p_{fs} is the probability that a participant uses the app the day after not using the app and p_{ss} is the probability that a participant uses the app the day after using the app. These probabilities will be calculated for participants who initiate use of the app, from that time until their last use.

(2)

$$PCI = \frac{p_{fs}/(1 - p_{fs})}{p_{ss}/(1 - p_{ss})}$$

3. Data analysis plan – inferential analysis

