3.1.4. Dose-response analysis

A dose-response analysis will be used to test usage as a mediator of each outcome. Multiple measurements of usage were collected and are listed in Appendix A. Metrics specified in section 2.3 will be created by assessing whether the participant used any app activity on a given day. Logging into the app without activity will not count as app usage because this information was not collected for the full study period. Activity use is also more likely to be associated with engagement with the app than is login alone. Daily usage and weekly usage will be the dependent variables for the dose-response models. As an exploratory analysis, the PCI may be analyzed as a dependent variable. The dose-response relationship will be analyzed for the primary and secondary outcomes using a multiple linear effects model and the confounder adjustment method (12). The model for adherence will be created using 20% of the unblinded data. The dose-response effects for the primary outcome will be reported in the manuscript. The dose-response effect for the secondary outcomes will be reported in the supplemental material.

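### Equation 2 for the patient cooperativity index runs in the opposite direction to the sentence that explains it

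*SAP*

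**What the plan says.** SAP section 2.7 introduces the PCI as an odds ratio meant to reflect long breaks in app use. Four statements matter.

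- Interpretation (section 2.7): "participants with a higher PCI are more likely to use the app one day after using it the previous day".
- First probability (section 2.7): p_fs "is the probability that a participant uses the app the day after not using the app".
- Second probability (section 2.7): p_ss "is the probability that a participant uses the app the day after using the app".
- Equation 2 (section 2.7): the odds of p_fs form the numerator and the odds of p_ss the denominator.

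Both probabilities are taken over the period from a participant's first use to the last. Section 3.1.4 then gives the index a possible inferential role: "As an exploratory analysis, the PCI may be analyzed as a dependent variable". Nothing elsewhere in the SAP restates or corrects its direction.

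**The concern.** The interpretive sentence makes the PCI rise with p_ss. The equation makes it fall with p_ss. The sentence, the two definitions and the equation cannot all be right.

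The risk is a misread sign in the exploratory dose-response analysis. Section 2.5 divides the work: one analyst runs the outcome models on the full data and another interprets the reported results. The first could follow the equation while the second follows the sentence. A reversed index still gives plausible positive values, so nothing in the output need reveal the mismatch.

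**Working it through.** **Inputs.** The definitions of p_fs and p_ss, equation 2 and the interpretive sentence all come from SAP section 2.7. The SAP reports no PCI value and no value for either probability, so there is no planned figure to reproduce. The probabilities below are assumptions for illustration.

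**Step 1: direction of the printed formula.** Write odds(p) = p/(1 − p), which increases with p. Equation 2 is

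PCI = odds(p_fs) / odds(p_ss).

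For a fixed p_fs strictly between 0 and 1, raising p_ss raises the denominator, so the PCI falls. A check on a grid from 0.01 to 0.99 for both probabilities found a strict fall at every fixed p_fs. The inverted ratio, odds(p_ss)/odds(p_fs), rose strictly on the same grid.

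**Step 2: the comparative reading.** Since the PCI is called an odds ratio, the sentence could mean that use is more likely after a use day than after a non-use day. That is p_ss > p_fs, which implies odds(p_ss) > odds(p_fs) and so a printed PCI below 1. The conflict remains under this reading.

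**Step 3: size, at p_fs = 0.1.**

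- p_ss = 0.8: printed (0.1/0.9)/(0.8/0.2) = 0.1111/4 = 0.028; inverted 36.
- p_ss = 0.2: printed (0.1/0.9)/(0.2/0.8) = 0.1111/0.25 = 0.44; inverted 2.25.

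**Step 4: range over assumed values.** Each cell shows printed / inverted.

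| p_fs | p_ss = 0.2 | p_ss = 0.5 | p_ss = 0.8 | p_ss = 0.9 |
|---|---|---|---|---|
| 0.1 | 0.44 / 2.25 | 0.111 / 9 | 0.028 / 36 | 0.012 / 81 |
| 0.2 | 1 / 1 | 0.25 / 4 | 0.0625 / 16 | 0.028 / 36 |
| 0.5 | 4 / 0.25 | 1 / 1 | 0.25 / 4 | 0.111 / 9 |

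Along every row the printed index falls and the inverted index rises.

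**Step 5: effect on an association.** The two forms are exact reciprocals, so log(inverted) = −log(printed) and the ranks are reversed. A log-scale coefficient or a rank correlation therefore keeps its size and changes sign. In a simulated set of 5,000 users, the correlation between the two forms was −1 on both scales.

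**Step 6: where the ordering stops.** Let p_fs differ between two users.

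- User A, p_ss = 0.9 and p_fs = 0.8: printed (0.8/0.2)/(0.9/0.1) = 4/9 = 0.44; inverted 2.25.
- User B, p_ss = 0.2 and p_fs = 0.05: printed (0.05/0.95)/(0.2/0.8) = 0.0526/0.25 = 0.21; inverted 4.75.

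User A has much the higher p_ss, yet scores higher on the printed form and lower on the inverted one. Likewise p_fs = p_ss = 0.8 gives 1 in both forms. The index is a contrast between two conditional odds, not a measure of how much someone uses the app.

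**The case against.** The strongest reply is that the sentence is only a loose gloss on a ratio and that little depends on it. Much of this stands.

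- A reader might infer that persistent users always score lower under equation 2. Step 6 shows that this holds only at equal p_fs. It also shows that inverting the ratio does not make the sentence true for every pair of users, so the wording needs attention whichever way the ratio is written.
- A reader might infer that every PCI result would be reversed. Exact reversal applies to rank and log-scale analyses. Section 3.1.4 plans a multiple linear effects model and mentions no log transformation. On the raw scale an index and its reciprocal need not give linear associations of opposite sign.
- The index is optional in both places where it appears: section 3.1.4 says only that "the PCI may be analyzed as a dependent variable". Daily and weekly usage are the planned dose-response measures.
- A reader might also want a rule for probabilities of 0 or 1, such as a continuity correction. The SAP does not say how the probabilities are estimated, so how often such values arise cannot be judged. A user with no non-use day in the window has no data on p_fs, and a correction would not supply any. That question is not part of this point.

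The reply does not remove the contradiction. At fixed p_fs, and under the comparative reading, the equation and the sentence still disagree.

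**Conclusion.** The point stands as a minor internal contradiction in section 2.7. Equation 2 and its stated interpretation point in opposite directions at any fixed p_fs, and a participant with p_ss > p_fs scores below 1 where the sentence implies a high score. The direction follows from the formula alone; the illustrative sizes rest on assumed probabilities.

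A wrong conclusion requires that the optional metric is computed, that it is computed as printed, and that it is read by the sentence. Rank or log-scale associations would then be interpreted with the wrong sign. The documents do not support any wider claim: the primary and secondary treatment comparisons do not use the PCI. Nor do they show which side is the slip, because the source cited for the index is not available here.

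**What to change.** Before the metric is computed, make equation 2 and the sentence agree in one of two ways:

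- define PCI = [p_ss/(1 − p_ss)] / [p_fs/(1 − p_fs)] and keep the stated direction; or
- keep equation 2 and reverse the sentence, so that a higher value means relatively more use after a non-use day.

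In either case, describe the PCI as comparing the odds of use after a use day with the odds of use after a non-use day, and say that it does not measure overall persistence. The sponsor can check the orientation against its cited source. The cost is a short edit to section 2.7, with no new data and no change to any other analysis.

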3.1. Main analyses of treatment differences

The main analysis compares the mean gestational weeks at birth between the MHP and usual care cohorts. An estimate of the average treatment effect, 95% confidence interval, and effect size will be reported. EG will remain blind to the 80% of outcome data not used to set the terms of the analysis (Section 2.5).

The primary and secondary outcomes will be evaluated at the 5% significance level. No correction for chance will be used for the primary outcome, as there is only one test. For the 9 secondary outcomes, we will report both corrected and uncorrected p-values, using the Bonferroni correction to reduce risk of reporting a false positive result. As a sensitivity analysis, the Bonferroni corrected p-values for ten outcome values will be reported in the supplemental material of the report.

All tests will include all participants with data on the outcome measure involved.

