Some collected covariates are specific to this dataset. One is hospital location, which may capture differences in resources, practices, and patient populations. The second is the date of the first visit recorded in Epic, which may capture factors like access to care or social conditions (e.g., the pandemic). We will include hospital location as a variable in all models. We will not include date of first visit as it might be correlated with ones that affect the effectiveness of the app over time.

Residual plots will be used to evaluate the models for heteroskedasticity and the need for using robust standard errors, in order to allow for violations in the assumption that observations are independent and identically distributed (8).

Differences between the cohorts will be described using adjusted mean differences and p-values. Results will be considered significant at $p < 0.05$.

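### The plan does not expressly say whether corrected or uncorrected p-values decide the nine secondary outcomes, and Holm would serve better than Bonferroni

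*SAP*

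**What the plan says.** Four statements in the SAP bear on this point.

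- **Level.** Section 3.1: "The primary and secondary outcomes will be evaluated at the 5% significance level".
- **Correction.** Section 3.1 exempts the primary outcome: "No correction for chance will be used for the primary outcome, as there is only one test". For the secondary outcomes it states "we will report both corrected and uncorrected p-values, using the Bonferroni correction to reduce risk of reporting a false positive result".
- **Further set.** Section 3.1 adds, as a sensitivity analysis, that "the Bonferroni corrected p-values for ten outcome values will be reported in the supplemental material".
- **Decision rule.** The last paragraph of section 3.1.1, on the primary outcome, gives the only explicit rule: "Results will be considered significant at $p < 0.05". Section 3.1.2 then has the secondary analyses follow the procedures of the primary one.

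Section 3.1.1 also plans two models for each outcome. One adjusts only for confounders known from the literature, and the other adds confounders found empirically. The SAP does not say which model's p-value enters the correction.

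**The concern.** Each secondary outcome will appear in the report with an uncorrected p-value and a nine-fold corrected one, and the threshold is 0.05. The plan never expressly ties the threshold to either value. When the two fall on opposite sides of 0.05, the choice could be made after the results are known, which prespecification is meant to prevent. If the uncorrected values were used, the correction would be shown in the table but would protect nothing.

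There is a second, smaller point. If the corrected values are used, as seems intended, single-step Bonferroni is not the best choice for the purpose. Holm's step-down version gives the same guarantee and can only reject the same hypotheses or more.

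**Working it through.** **Inputs from the SAP.** Level 0.05 (section 3.1); nine secondary outcomes with Bonferroni (section 3.1); a ten-outcome set as a sensitivity analysis (section 3.1); two models per outcome (section 3.1.1); cohorts of 7147 and 5197 deliveries, SD 10 days, 80% power and a detectable difference of 0.51 day (section 1.5).

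**Assumptions.** The SAP gives no effect sizes or correlations for the secondary outcomes, so those used below are assumed.

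**1. Sidedness.** The SAP does not state it, so it is inferred from the plan's own power figure.

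- Detectable effect = (z for alpha + z for power) × sqrt(1/7147 + 1/5197), and the square root is 0.01823.
- Two-sided: (1.960 + 0.842) × 0.01823 = 0.0511 SD, or 0.51 day. This reproduces the plan.
- One-sided: (1.645 + 0.842) × 0.01823 = 0.0453 SD, or 0.45 day. This does not.

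Two-sided tests at 0.05 are used from here on.

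**2. The zone left open.** Bonferroni over nine compares each uncorrected p-value with 0.05/9 = 0.00556. An uncorrected value between 0.00556 and 0.05 is significant on one reading and not on the other.

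**3. Familywise error on each reading.**

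- Uncorrected, nine independent true nulls: 1 − 0.95^9 = 0.370.
- Uncorrected, nine true nulls with an assumed common correlation (simulated): 0.327 at 0.3 and 0.269 at 0.5.
- Uncorrected, with some effects real, the error applies only to the remaining nulls. Independent: 1 − 0.95^6 = 0.265 with three real, 1 − 0.95^4 = 0.185 with five, and 1 − 0.95^2 = 0.098 with seven.
- Bonferroni: at most 9 × 0.00556 = 0.05; with nine independent true nulls, 1 − (1 − 0.00556)^9 = 0.049.

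**4. Holm against Bonferroni.** Holm orders the nine p-values and compares them in turn with 0.05/9, 0.05/8, …, 0.05/1, that is 0.00556, 0.00625, 0.00714, 0.00833, 0.0100, 0.0125, 0.0167, 0.025 and 0.05. It stops at the first failure. The first threshold equals Bonferroni's and the later ones are larger, so Holm rejects everything that Bonferroni rejects. Its familywise error is also at most 0.05 under any dependence.

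The table gives average power per real effect, Bonferroni → Holm, from 200,000 simulated sets of nine independent two-sided z-tests. A mean z of 2.80 corresponds to 80% power for a single uncorrected test.

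| Real effects | mean z = 2 | mean z = 2.80 | mean z = 3 |
|---|---|---|---|
| 1 | 21.9 → 21.9% | 51.0 → 51.1% | 59.2 → 59.3% |
| 3 | 22.0 → 22.6% | 51.1 → 52.9% | 58.8 → 60.8% |
| 5 | 22.0 → 23.2% | 51.1 → 55.0% | 58.9 → 63.2% |
| 9 | 21.9 → 24.7% | 51.1 → 62.5% | 59.0 → 72.3% |

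In no replicate did Holm miss a Bonferroni rejection. The gain is nil or negligible with one real effect, about 1 to 4 points with three to five, and about 3 to 13 points with all nine.

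**The case against.** **The intent is fairly clear.** The correction is described as "using the Bonferroni correction to reduce risk of reporting a false positive result" and is contrasted with a primary outcome that needs none. The natural reading is that corrected values govern and uncorrected ones are shown for transparency. The rule at 0.05 sits in the primary-outcome section and fits an adjusted p-value as well as an unadjusted one. Most of this stands, and it keeps the point small. But a stated purpose is not a decision rule, and section 3.1.2 carries over the procedures of a primary outcome that is uncorrected. The opposite reading could still be defended.

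**Bonferroni is valid.** This stands in full. A reader might infer that its use is an error, but the document does not support that: the method is prespecified and controls the familywise error. Holm is a gain in efficiency, and a negligible one if only one effect is real.

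**The 37% is a worst case.** This also stands. It needs nine independent true nulls, and some of these outcomes are evidently related: two concern attendance at prenatal appointments, and depression and anxiety share their listed confounders. The figure should also not be paired with the power gains, which assume that several effects are real.

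**The ten-outcome set is not a third criterion.** A reader might infer three competing p-values. Section 3.1 already labels this set a sensitivity analysis for the supplement, so only the first two compete.

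**Holm is not free of cost.** Bonferroni has simple matching simultaneous confidence intervals, and Holm's are less simple. That is a real trade-off in general, but this plan specifies no multiplicity-adjusted intervals.

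**Conclusion.** The point holds as a minor one. Section 3.1 does not expressly name the p-value that decides a secondary claim, which leaves uncorrected values from 0.0056 to 0.05 open to either reading. The familywise error is at most 5% if the corrected values decide. If the uncorrected ones do, it is up to about 37%, or about 27% with nine true nulls at an assumed correlation of 0.5. The plan does not commit to the uncorrected reading, so 37% is not the plan's error rate; it is what the missing sentence would permit.

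Holm is the better procedure for the stated aim, with the same bound and no lost rejections. Its advantage of about 0 to 13 points of average power depends on assumed effects and independent tests, and is material only if several of the nine effects are real. The primary analysis is not affected.

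**What to change.** Add to section 3.1, before the cohort labels are unblinded:

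- Claims of significance for the nine secondary outcomes rest only on Holm-adjusted p-values at 0.05 (two-sided).
- These p-values come from one named model of the two described in section 3.1.1, the same for all nine outcomes. Without this, each outcome still has two candidate p-values.
- Unadjusted p-values are descriptive.
- The ten-outcome set remains a sensitivity analysis and decides no claim.

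If the sponsor prefers to keep Bonferroni, the other three statements are still needed, with the Bonferroni-corrected value named as the deciding one.

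The cost is a few lines of text and a change of the method argument in R's p-value adjustment function. No new data are needed. The one small drawback is the less simple simultaneous intervals, which would matter only if such intervals were added to the plan.

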3.1.1. Analysis of primary outcomes

The difference in gestational weeks at birth will be evaluated using a linear effects model accounting for confounders of preterm birth, as measured at baseline. We estimate that about 57 out of 12,344 deliveries are for a second pregnancy for participants included in the sample given that 0.464% of participants who downloaded the app had two deliveries in the sample. We have included these women in the sample because we cannot exclude similar women in the usual care cohort given limitations in our data. Likewise, we cannot account for random effects of multiple deliveries using a mixed effects model.

Baseline study variables will be included as confounders in the model if (a) the literature has identified the variable as a confounder of preterm birth risk and (b) they might plausibly have influenced participants' decision to download the app. If, for a variable, the evidence on condition (a) is inconclusive and condition (b) is possible, we will examine the data and include the variable if it passes a 10% change-in-estimates threshold for the outcome or for the likelihood of downloading the app. The change-in-estimate will be calculated by adding each study variable to the model from the literature individually. Only baseline variables will be evaluated as potential confounders, as they could not have been affected by use of the app.

We will report the results of two models for each outcome, one using only confounders identified in the literature and one adding confounders identified empirically (Appendix A). Including fewer confounders will reduce the likelihood that the average treatment effect applies only to an unrepresentative subset of the population. Including additional confounders will reduce the likelihood of statistical bias in estimating the average treatment effect.

The dataset contains many known confounders of preterm birth that could be included in the model including:

- Previous preterm birth (3)
- Race (3)
- Low body-mass index (3,4)
- Insurance type (5)
- Area deprivation index (6)
- Multiple gestations (3)
- Previous spontaneous abortions (7)
- Hypertension (3)
- Diabetes (3)
- Tobacco use (3)

There are also many known predictors of preterm birth that are not in the EHRs, hence not available for this study. They include educational attainment, marital status, interpregnancy interval, relatives who delivered preterm, and genetic predictors of preterm birth (3).

Some collected covariates are specific to this dataset. One is hospital location, which may capture differences in resources, practices, and patient populations. The second is the date of the first visit recorded in Epic, which may capture factors like access to care or social conditions (e.g., the pandemic). We will include hospital location as a variable in all models. We will not include date of first visit as it might be correlated with ones that affect the effectiveness of the app over time.

Residual plots will be used to evaluate the models for heteroskedasticity and the need for using robust standard errors, in order to allow for violations in the assumption that observations are independent and identically distributed (8).

Differences between the cohorts will be described using adjusted mean differences and p-values. Results will be considered significant at $p < 0.05$.

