1.5. Sample Size Justification

Due to the observational nature of the study and recruitment context, it was not possible to predetermine the sample size based on statistical power for estimating the primary and secondary outcomes. Instead, all participants who met the inclusion criteria between September 2019 and February 2022 were included. The final sample has 12,344 deliveries, divided between the MHP and usual care cohorts (with 7147 in one and 5197 in the other, with their identities currently blinded). This represents about 12,287 different participants (we only have information about the percent of multiple deliveries for participants who downloaded the app, 0.464%). Given the sample sizes in the two cohorts, there is 80% power to detect an effect size of 0.051 days. Assuming that the outcomes are normally distributed with a standard deviation of 10 days (1), the study has 80% power to detect a 0.51 day difference in gestational age at birth between the cohorts.

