3.1.2. Analysis of secondary outcomes

Analytical procedures for the secondary outcomes will follow those for the primary outcome. Each outcome will have its own appropriate confounders. As with the primary outcome, these confounders will be based on previous research and specified a priori. As needed, they will be supplemented by empirical analysis of the 20% subset, including baseline covariates specified in Appendix B, with a 10% change-in-estimate threshold for inclusion.

These confounders from the literature are available:

1. Preterm birth defined as delivery before 37 gestational weeks.
 - a. Same confounders as the primary outcome
2. Clinical diagnoses of depression.
 - a. History of anxiety and depression (9)
 - b. Smoking (9)
 - c. Past pregnancy complications or loss (9)

Unavailable: Lack of partner or social support or having a problematic relationship, a history of abuse or child abuse, having had an unplanned or unwanted pregnancy, perceived stress, cognitive style (including “pessimism, anger and rumination; a tendency to be nervous, worried or shy; low self-esteem and low self-efficacy; and high levels of neuroticism or psychoticism”), and single marital status (9).
3. Anxiety rates (using ICD10 codes).
 - a. History of anxiety and depression (9)
 - b. Smoking (9)
 - c. Past pregnancy complications or loss (9)

Unavailable: Same as anxiety (9).
4. Referral to behavioral health
 - a. No confounders identified
5. Referral to social work
 - a. No confounders identified
6. Preeclampsia
 - a. Prior pre-eclampsia (10)
 - b. Chronic hypertension (10)
 - c. Pre-gestational diabetes (10)
 - d. BMI >30 (10)

Unavailable: Antiphospholipid antibody syndrome (10).
7. Sufficient gestational weight gain
 - a. Pre-pregnancy BMI (11)
 - b. Age (11)

Unavailable: Family violence; marital status; food insecurity; maternal pregravid metabolic status; hyperemesis gravidarum; anorexia; past bariatric surgery (11).
8. Number of prenatal appointments attended
 - a. No confounders identified
9. Percent of required prenatal appointments attended
 - a. No confounders identified

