Appendix A

Covariates and Outcomes

Variable Name in EHR	Description	Variable type
PATIENT_ID	ID for each patient not related to patient information	ID
MOM_AGE	Mother's age at time of delivery	Baseline covariate
FINANCIAL_CLASS	Payor at time of delivery from Medipac (insurance level, might be like coverage) (i.e. name like 'UPMC HEALTH NETWORK', 'MED PLUS', 'BEST HEALTH CARE', etc)	Baseline covariate
HOSP_ROLLUP_GROUPING1	Payor at time of delivery from Medipac (insurance type) (i.e. specifies type of UPMC insurance, examples include 'UPMC Commercial', 'Other MA Managed', 'Other Commercial', etc)	Baseline covariate
HOSP_ROLLUP_GROUPING2	Medicare, Medicaid, Self-pay, or Commercial Insurance	Baseline covariate
HPFLAG	Payor at time of delivery from Medipac (UPMC Health Plan Member flag, 1= has UPMC Health Plan, 0=Doesn't have it)	Baseline covariate
PT_ZIP	Patient zipcode	Baseline covariate
AD_ZIP_4	Patient zipcode, location extension (+4)	Baseline covariate
ADI_NATRANK	Area deprivation index, national ranking (0 most deprived, 100 least deprived)	Baseline covariate
RACE	Race, as reported through UPMC	Baseline covariate
MOM_HEIGHT	mother's height at time of delivery (cm)	Baseline covariate
OB_GRAVIDITY	Number of pregnancies (includes current pregnancy, so if it's their first pregnancy, this will be a 1)	Baseline covariate
OB_PARITY	Number of previous deliveries (will be 0 if it's their first pregnancy)	Baseline covariate
OB_FULL_TERM	Number of previous full term pregnancies	Baseline covariate
OB_PREMATURE	Number of previous premature deliveries (prior to 37 gestational weeks)	Baseline covariate
OB_ABORTIONS	Number of previous abortions, including therapeutic/spontaneous abortions	Baseline covariate
OB_LIVING	Number of previous live deliveries	Baseline covariate
OB_SPONTANEOUS_AB	Number of previous miscarriage/spontaneous abortions	Baseline covariate
OB_THERAPEUTIC_AB	Number of previous therapeutic abortions	Baseline covariate
PREGRAVID_WEIGHT	mother's pre-pregnancy weight (kg)	Baseline covariate
GESTAGE_ATVISIT_DAYS	This is the gestational age of the pregnancy at the time of prenatal visit. Calculated using the estimated delivery date ((280-(EPISODE.OB_WRK_EDD_DT-pat_enc.contact_date))).	Baseline covariate
PREGSTART_OBESE	Obese BMI at first prenatal visit (binary variable)	Baseline covariate
PREGSTART_MORBIDOBSE	Morbidly obese BMI at first visit (binary variable)	Baseline covariate

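### Parity, maternal age and BMI above the low range are not named as a priori covariates for gestational age, so adjustment for them is not guaranteed, and the literature-only model can carry a parity imbalance into the app estimate

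*SAP*

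**What the plan says.** SAP section 3.1.1 states that the difference in gestational age will be "evaluated using a linear effects model accounting for confounders of preterm birth, as measured at baseline". A baseline variable enters if the literature identifies it as a confounder of preterm birth risk and it could plausibly have influenced downloading. Where the literature is inconclusive, a 10% change-in-estimate screen on the unblinded 20% subset decides.

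The named list opens with "The dataset contains many known confounders of preterm birth that could be included in the model including". It holds previous preterm birth, race, low BMI, insurance type, area deprivation, multiple gestation, previous spontaneous abortion, hypertension, diabetes and tobacco use. Parity, maternal age and higher BMI are neither on it nor among the predictors described as unavailable. Appendix A nevertheless lists OB_PARITY ("Number of previous deliveries (will be 0 if" it is a first pregnancy), MOM_AGE, PREGSTART_OBESE and PREGRAVID_WEIGHT as baseline covariates.

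Two models are reported for each outcome: one with literature confounders only, one with empirically selected confounders added. Section 3.1 says the primary outcome involves a single test, but neither section says which model supplies it.

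In section 3.1.2, age is named only for gestational weight gain. The preeclampsia list ("Prior pre-eclampsia (10"), chronic hypertension, pre-gestational diabetes and BMI above 30) has no parity, age or plurality.

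**The concern.** The cohorts are self-selected by downloading, so the covariate set carries much of the causal claim. First-time mothers may well download a pregnancy app at a different rate, and may differ in gestational length. If both hold, a model without parity attributes part of that difference to the app.

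Two features of the plan add to this. First, the outcome is mean gestational age over all births, but the selection rule is framed around preterm birth risk. A variable that shifts length of gestation at term with little effect before 37 weeks can fail that rule. Second, the obstetric history terms do not identify first-time mothers: a woman in her first pregnancy has no previous preterm birth, exactly like a parous woman whose births were all at term. Prior preeclampsia has the same property in the preeclampsia model.

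**Working it through.** **Inputs from the SAP.** Cohort sizes ("with 7147 in one and 5197 in the other, with their identities currently blinded") and the SD ("Assuming that the outcomes are normally distributed with a standard deviation of 10 days") are in section 1.5. The significance level is in section 3.1 ("The primary and secondary outcomes will be evaluated at the 5% significance level"), taken here as two-sided.

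**Step 1: reproduce the plan's figure.**
- SE = 10 × √(1/7147 + 1/5197) = 0.182 days.
- Detectable difference = (1.960 + 0.842) × 0.1823 = 0.511 days. This agrees with section 1.5: "the study has 80% power to detect a 0.51 day difference in gestational age at birth between the cohorts".
- Smallest significant difference = 1.96 × 0.1823 = 0.357 days.

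A bias of a few tenths of a day is therefore material.

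**Step 2: bias from an omitted parity term.** The SAP gives neither a parity effect nor a cohort difference in the share of first-time mothers, so both are assumed. With no app effect:
- b = (parity effect in days) × (difference in nulliparous share)
- false-positive rate = Φ(b/SE − 1.96) + Φ(−b/SE − 1.96)

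| Gap × effect | b (days) | False-positive rate |
|---|---|---|
| 5 points × 1 day | 0.05 | 5.9% |
| 10 points × 1 day | 0.10 | 8.5% |
| 10 points × 2 days | 0.20 | 19.5% |
| 15 points × 3 days | 0.45 | 69.4% |

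**Step 3: the same with previous preterm birth in the model.** Further assumptions: 40% nulliparous; 10% of parous women with a previous preterm birth, at −9 days. Gestational age was simulated and regressed on cohort and previous preterm birth, with and without a nulliparity term.

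| Gap × effect | Bias without parity | Rejection without parity |
|---|---|---|
| 5 points × 1 day | 0.05 days | about 5% |
| 10 points × 2 days | 0.19 days | about 18% |
| 15 points × 3 days | 0.43 days | about 64% |

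With the nulliparity term, absolute bias was at most about 0.015 days and rejection about 5% throughout. Comparing steps 2 and 3, the history term removes almost none of the parity bias (0.20 falls only to 0.19; 0.45 only to 0.43).

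**Step 4: would the 10% screen add parity?** The subset has 0.20 × 12,344 ≈ 2,469 deliveries, about 1,234 per cohort under the even split in section 2.5. The app estimate there has SE = 10 × √(2/1234) ≈ 0.40 days. The threshold is a tenth of that noisy estimate: 0.051 days if it is 0.51, but 0.13 days if it happens to be 1.3, so a 0.10-day bias would then be missed. Simulated miss rates:
- 15 points × 3 days: about 0% with no app effect.
- 10 points × 2 days: about 0.4% with no app effect, about 2% with a true effect of 0.51 days.
- 10 points × 1 day: about 10%, 30% and 60% with true effects of 0, 0.5 and 1 day.
- 5 points × 1 day: about 33% with no app effect, about 60% with 0.51 days.

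These runs count only the change in the outcome estimate. The SAP also lets a variable enter through its relation to downloading.

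**The case against.** The strongest reply is that the SAP does not shut parity out, and that is right. The list is worded as open. The inclusion rule admits any variable the literature supports, and the 10% screen handles inconclusive ones. Section 3.1.5 builds the propensity score from baseline confounders related to both treatment and outcome, a criterion parity would meet on the premise used here. A reader might infer that parity, age and obesity are excluded from adjustment, or that the propensity score must share the gap. The text supports neither.

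A reader might also take 18% or 64% as the trial's false-positive rate. Step 4 shows otherwise: in those scenarios, with no app effect, the screen adds parity to the second model almost every time. The figures belong to the literature-only model as listed.

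It is also fair that the parity effect, nulliparous share and imbalance are assumptions, that age, high BMI and preeclampsia were not quantified, and that hypertension and diabetes, which are listed, may carry part of any obesity effect.

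What remains is that every one of these routes depends on a later judgement or a noisy screen. The literature-only model is reported whatever the screen finds, and nothing prevents it from supplying the primary p-value. Section 3.1.2 describes the confounders as fixed in advance, as for the primary outcome, and an open list does not do that.

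**Conclusion.** The point holds in this form: adjustment for parity, maternal age and BMI above the low range is not guaranteed in the primary analysis, although the variables are in Appendix A. The literature-only model as listed is exposed to a parity imbalance. On the assumptions above, the bias runs from 0.05 to 0.43 days against a detectable difference of 0.51 days, and the false-positive rate from about 5% to 64%, with 0.19 days and 18% in the middle case. The low end is harmless.

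The second model is largely protected when the bias is large. It is less dependable when the bias is about 0.1 day or less, especially if the app estimate is not near zero. Nothing in the SAP shows that an imbalance exists, how large it is or which way it would act. This is a free improvement, not evidence that the planned result will be wrong.

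**What to change.** In section 3.1.1, name nulliparity (from OB_PARITY), MOM_AGE and BMI over its full range as a priori covariates. Put them in both reported models for gestational age and for preterm birth, and in the propensity score. Close the list, and state which of the two models is the single primary test.

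In section 3.1.2, add parity, MOM_AGE and SINGLETONS to the preeclampsia model.

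Separate three-level coding of obstetric history is not needed: once nulliparity is in the model, a binary history item and the nulliparity indicator already define the three groups.

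The cost is a change of SAP wording and a few degrees of freedom out of 12,344 deliveries. The variables are already listed in Appendix A, and the stated 0.51-day detectable difference is essentially unaffected.
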